the app. After signing their consent forms, all participants will be given access to the app (via a username and password); however, initially they will only have access to the resource sheet (providing local resources) along with consent forms, including forms for parental consent. Parents/guardians will be able to sign the consent via the app. All consent forms will be filed and stored separately from other app and survey data. Parental consent forms will be available in both English and Spanish.

Baseline and follow-up questionnaires will take approximately 45 minutes and will be self-administered via an online survey. During an initial orientation, as time permits, participants will take the online baseline survey during that time. The online surveys can be taken by participants on their own as well. If participants take the baseline survey on their own, participants will be encouraged to complete the questionnaire in a safe and private location. In cases where participants do not complete the app-based questionnaire on-time or need assistance, staff will provide assistance and offer to meet participants to complete the survey in-person. The survey requires an ID, which will be provided to participants. Upon completion, questionnaire data will not be accessible via the online platform nor the mobile device.

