**Randomization and Retention.** Each group (n=18) will be randomized to study condition. Randomization will be stratified by site type (i.e. we will randomly assign an equal number of high schools to be in the treatment group and control group; we will do the same for community colleges and community-based partnerships). Participants randomized to the *Girls Invest* intervention will be notified with a brief orientation on how to use the app with contact information for study staff in case they have questions. App-based data on completion of modules and completion time will also be collected. Control group participants will be notified that they will be on the wait-list and complete the intervention after 6 months. Regardless of study condition, all participants will be linked to the online application for their savings accounts (ID can be uploaded online as well) upon completion of the baseline survey. For participants in the control group, accounts will become active after the 6 months follow up survey is complete. To maximize retention, incentive payments will be escalated: \$25 at baseline and \$30 at 6 months follow-up via Amazon e-cards. Participants will also be contacted via the app (or a phone call by study staff) every two months to update contact information. Those who do not complete follow-up questionnaires via the app will be contacted up to 4 times followed by contacting participant's alternate contacts, using methodology we have used effectively in previous studies. If these efforts are not successful, participants will be classified as non-respondents. Using similar tracking methods, our previous work with a similar sample achieved a 92% retention rate at 6 months follow-up.

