**Assessing the feasibility, fidelity, acceptability, and scalability of *Girls Invest* (Aim 1).** Data logs will serve to monitor study progress in recruitment (e.g. proportion eligible, interested, refused, and ability to recruit at least 1 friend), participant retention (e.g., differential dropouts by condition), adherence (e.g., savings account enrollment), and adverse events. Information on recruitment and retention (as well as intra-cluster correlation of endpoints within social networks) will help inform sample size determination for a subsequent full-scale trial. Contamination will be assessed via items on the follow-up survey (e.g. control participants' knowledge of *Girls Invest* or any participants in the *Girls Invest* intervention). App-generated data will assess engagement with and completion of *Girls Invest* (e.g. # modules completed, time spent on each) and used to identify completers (80% of the *Girls Invest* modules) versus non-completers.

Evaluation of acceptability and receptivity will include in-depth interviews (up to n=30; similar proportions index participants and peers, 5 with non-completers) to evaluate participants' experiences with *Girls Invest* (e.g. content, app dynamics, savings account features), and identify mechanisms underlying any intervention effects (e.g. did the intervention affect

economic vulnerability? how did these effects influence girls' sexual and contraceptive decision-making? Were certain components most impactful?) These will take place via a phone or online call or in private space at La Maestra. Based on our previous work, we expect 20 interviews to be sufficient for saturation of themes; however, we will conduct additional interviews (up to an additional 10) if needed. Participants will be paid \$30 for in-depth interviews. For those participants who are <18 years of age, we will obtain parental consent using the main study consent form, rather than using a separate form for in-depth interviews. Details of the in-depth interviews will be provided in these main study parental consent forms. While details are included in the main study consent form for participants, we will also review all of the in-depth interview procedures and details in a separate consent form provided immediately prior to the in-depth interview.

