**Statistical Power and Analyses on Economic, Social, and Health Behavior Risks. (Aim 2)**

Sample size calculation is based on intermediate outcomes (Figure 1) with at least 25% prevalence at baseline. To achieve 80% power, we will require 208 participants (approximately 13 in each of 16 groups) to be able to determine a moderate effect size of 0.52 (26% difference between the two arms on intermediate factors in Figure 1), using an intra-class correlation coefficient (ICC) of 0.03 given the group structure, type I error of 0.025, and 20% attrition (conservatively estimating 80% retention over 6 months). Note the sample size has taken multiple comparisons (using Bonferroni adjustment) into account. In addition, we may likely have a lower ICC, which would afford greater statistical power.

To assess clustering within groups (n=18), random effects models will calculate ICCs. We will conduct intent-to-treat analyses using crude and adjusted mixed effects logistic and linear regression models with a focus on intermediate variables (Figure 1) to assess group-by-time effects, with adjustments for clustering and intervention engagement and completion. To assess random imbalances (at baseline) and differences in attrition by condition, we will perform chi-square analyses and t-tests. We will adjust for relevant covariates to address imbalances between conditions. Differences in attrition between study conditions will be noted as potential threats to validity. We will also explore variations in observed intervention effects by savings behaviors, module completion, as well as relevant factors identified via in-depth interview findings.

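### The intent-to-treat models for Aim 2 adjust for engagement and completion, which arise after randomisation; coding and primary model are unstated, and some codings remove or bias the effect of assignment

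*Combined protocol and SAP*

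**What the plan says.** The Aim 2 section (Statistical Power and Analyses) states: "We will conduct intent-to-treat analyses using crude and adjusted mixed effects logistic and linear regression models". The same sentence says that these models are "to assess group-by-time effects, with adjustments for clustering and intervention engagement and completion".

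The Aim 1 section says where the two variables come from: "App-generated data will assess engagement with and completion of" the programme. Its examples are the number of modules done and the time spent on each, and girls with 80% of modules are classed as completers. Both variables therefore exist only after randomisation and only through use of the programme.

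For the other arm, Randomization and Retention says: "Control group participants will be notified that they will be on the wait-list and complete the intervention after 6 months". The consent section also limits app access at the start ("initially they will only have access to the resource sheet"), but that applies to all participants just after consent, and I do not rely on it.

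The Aim 2 section lists a separate analysis: "We will also explore variations in observed intervention effects by savings behaviors, module completion". So the adjustment in the intent-to-treat sentence is not simply that exploration under another name.

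The plan does not say:
- what value controls take on the two variables
- whether the terms are constant, time-varying or interacted with time
- whether the crude models leave them out
- whether the crude or the adjusted model is primary

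**The concern.** An intent-to-treat effect is the effect of being assigned to the programme. Module use is a consequence of assignment and also the route by which the programme is meant to work. A model that holds use fixed can estimate something else while keeping the intent-to-treat label. It can understate a real benefit. If girls who engage would have improved more in any case, it can show harm where there is none. With neither the coding nor the primary model stated, the result that counts can be settled after the data are seen. Aim 2 is the trial's powered comparison of outcomes.

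**Working it through.** **1. The plan's own figure.** Inputs from the Aim 2 section: 25% baseline prevalence, a 26-point difference (so 25% versus 51%), type I error 0.025, 80% power, ICC 0.03, 20% attrition, 16 groups. Taking 0.025 as two-sided (z = 2.241):

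- Per arm: [2.241·√(2·0.38·0.62) + 0.842·√(0.25·0.75 + 0.51·0.49)]² / 0.26² = 64.9, so 65.
- Retained group size: 208 × 0.80 / 16 = 10.4. Design effect: 1 + 9.4 × 0.03 = 1.282.
- Total: 130 × 1.282 / 0.80 = 208.3, against 208 stated.

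The sample size was thus computed for a plain two-arm difference with no engagement term.

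**2. What the group-by-time coefficient means.** Controls are coded zero.

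- *Main effect constant over time:* it cancels from the change over time, so the complete-data linear estimate does not move. Centring modules within the intervention arm also leaves it unchanged.
- *Completer flag by time:* the change in non-completers minus the change in controls.
- *Modules by time:* the contrast extrapolated to an intervention girl with zero modules.
- *Left missing in controls:* controls drop out and the arm contrast cannot be estimated.

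**3. How much is left when the programme works.** Assumed, not in the documents: true effect 0.52 on the SD scale, benefit linear in modules, and Beta-distributed module share. With the flag by time,

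what is left = 0.52 × (mean modules of non-completers / mean modules of all intervention girls).

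- Beta(4,1): 59% completers, 0.52 × 0.64/0.80 = 0.416.
- Beta(0.6,0.2): 63% completers, 0.52 × 0.389/0.75 = 0.270.
- Six further distributions: 0.259, 0.317, 0.416, 0.416, 0.434 and 0.468. The overall range is 0.26 to 0.47, with 18% to 80% completers.

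**4. Power.** 208 × 0.80 / 18 = 9.2, so take 9 groups of 9 analysed girls per arm (81 girls). Assume within-girl correlation 0.5 and half of the ICC specific to each wave. The variance of change is 2(1 − 0.5) = 1, of which 0.03 lies between groups. SE = √[2(0.03/9 + 0.97/81)] = 0.175, and power = Φ(0.52/0.175 − 2.241) = 77%. At correlations 0.3 and 0.7 the SE is 0.201 and 0.144, and power is about 63% and 91%.

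Simulated two-wave models (900 to 1,000 trials per scenario, variance components known, Beta(4,1) unless marked):

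| Term in model | Arm-by-time | SE | Rejection |
|---|---|---|---|
| None | 0.516 | 0.175 | 78% |
| Flag, main effect | 0.516 | unchanged | unchanged |
| Flag by time | 0.408 | 0.220 | 35% |
| Flag, time-varying | 0.410 | 0.210 | 40% |
| Flag by time, Beta(0.6,0.2) | 0.280 | 0.228 | 17% |
| Modules by time | −0.028 | 0.581 | 2% |
| Both by time | −0.021 | 0.813 | 3% |

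Over correlations 0.3 to 0.7, the 35% becomes 26% to 53%. If only half of the effect runs through use, a separate simulation leaves about 0.26 with modules by time and 0.46 to 0.47 with the flag. If all benefit falls in completers, the flag by time leaves 0.00.

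**5. No true effect, engagement prognostic.** If completers would improve by a gap *g* more than non-completers, and the arm's mean change equals that of controls, non-completers change by −(completer share × *g*). The gaps are assumed. At 60% completers (SE 0.212 to 0.223):

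- *g* = 0.2: −0.12, false positives 5%
- *g* = 0.3: −0.18, 8%
- *g* = 0.5: −0.30, 19 to 20%

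The nominal rate is 2.5%. Over the same gaps, bias is −0.08 to −0.20 (4 to 12%) at 40% completers and −0.16 to −0.40 (5 to 24%) at 80%. The sign reverses if completers would improve less.

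**6. Mixed logistic model, main-effect coding.** Prevalence is 25% in all cells except intervention completers at follow-up, who have 0.25 + 0.26/share. With a girl-level random intercept of SD 1.5, the log-odds ratio goes from 1.476 to 1.569 (+6.3%), 1.531 to 1.570 (+2.6%) and 1.565 to 1.579 (+0.9%) at 40, 60 and 80% completers. This is not a material harm.

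**The case against.** Five points can be made for the plan.

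- *The plainest reading is harmless.* A covariate described only as an adjustment is most naturally a main effect, and then a linear estimate does not move. This stands. It limits the claim to what the wording permits. But the sentence is about group-by-time effects, so a by-time term cannot be excluded, and under the harmless coding the term has no stated use.
- *Crude models are planned.* A crude model would ordinarily carry no covariates, so an unadjusted estimate will probably be reported. That is likely. Still, as written the adjustment clause follows both crude and adjusted models, and neither is named primary.
- *The sizes are assumed.* True: the documents give no module distribution, completer share, within-girl correlation or prognostic gap. The zero for modules by time follows from making benefit proportional to modules, and the zero for the flag follows from placing all benefit in completers. Another set-up, in which a latent trait drives both use and outcome, gave about −0.5 to −0.7 with modules adjusted. The size depends heavily on the assumptions; the change in what is estimated does not.
- *The power contrast is not the plan's own.* Also true. The 208 rests on two proportions; a standardised 0.52 at two-sided 0.025 would need 228 to 241. The drop from 77% to 35% illustrates the loss and is not a forecast for this trial.
- *The trial partly serves to plan a larger one.* That lowers the stakes somewhat, but Aim 2 is powered and tested here.

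**Conclusion.** The concern holds. The intent-to-treat sentence conditions on variables that follow randomisation and that controls cannot have before the 6-month survey. Depending on the coding, the adjustment either does nothing useful or changes the quantity estimated.

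That conclusion needs no assumption about engagement. The sizes do. They also rest on a linear outcome, a 0.52 SD effect and, for the power and false-positive figures, known variance components. Under by-time coding, the completer flag leaves roughly half to nine-tenths of the effect (0.26/0.52 = 50%, 0.47/0.52 = 90%) when benefit follows modules. Module count by time removes essentially all of it. Prognostic engagement can create an apparent effect with false-positive rates of about 4% to 24% over the scenarios tried. Material harm is not certain, because a main-effect coding or a crude primary model would avoid it. The plan commits to neither, so the text should be corrected before outcome data are examined.

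**What to change.** Remove engagement and completion from the adjustments in the intent-to-treat sentence and name one primary model. For example:

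> The primary analysis is a mixed effects logistic or linear model with arm, time and arm-by-time, and random effects for group and for girl. Participants are analysed as randomised. Adjustment is limited to site type and to covariates measured before randomisation. Engagement and completion are not included.

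State whether the crude model is this model without covariates. Keep engagement and completion for the exploration by module completion that the Aim 2 section already lists, or for a model labelled secondary and not intent-to-treat, with its coding and the value given to controls written down.

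The cost is a few sentences of analysis wording. No new data are needed and the sample size does not change.

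### Baseline covariates are chosen by observed imbalance, judged by tests with no stated allowance for the 18 randomized groups, and the baseline outcome is not fixed as a covariate

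*Combined protocol and SAP*

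**What the plan says.** The unit of randomization is the group: "Each group (n=18) will be randomized to study condition" (Randomization and Retention). The same section adds that "Randomization will be stratified by site type", the types being high schools, community colleges and community-based partnerships.

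The analysis text is the Aim 2 section on statistical power and analyses. It plans intent-to-treat analyses by "crude and adjusted mixed effects logistic and linear regression models with a focus on intermediate variables (Figure 1) to assess group-by-time effects". The adjustments it names for these models are worded as follows: "with adjustments for clustering and intervention engagement and completion". On imbalance and attrition the plan then states: "To assess random imbalances (at baseline) and differences in attrition by condition, we will perform chi-square analyses and t-tests". The only rule for baseline covariates comes next: "We will adjust for relevant covariates to address imbalances between conditions". On attrition it adds: "Differences in attrition between study conditions will be noted as potential threats to validity".

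Clustering is mentioned for the ICC calculation and the outcome models, but not for the chi-square and t-tests. The text gives no covariate list and no threshold for imbalance. It does not name site type, and it does not say how the baseline value of the outcome enters the model.

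**The concern.** Three things are at stake.

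- **An open model.** If covariates depend on which imbalances appear, the adjusted model is settled only after the data are in hand. The text does not say whether the crude or the adjusted result carries the conclusion.
- **A miscalibrated screen.** Girls in the same group tend to be alike. A test that treats them as independent flags too many chance differences between arms. The plan treats differential attrition as a threat to validity, so over-flagging could also overstate that threat.
- **Lost precision.** The baseline value of the outcome is collected anyway and is usually the strongest predictor of follow-up. Using it only as a first response, with arm means left free at baseline, gives a noisier effect estimate than conditioning on it.

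The named adjustments also include engagement and completion, which arise after randomization. On controls the plan says "Control group participants will be notified that they will be on the wait-list and complete the intervention after 6 months", so their completion is zero at the 6-month survey.

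**Working it through.** **1. The plan's own figure.** Inputs from the Aim 2 text: 25% baseline prevalence, 26-point difference (hence 51%), alpha 0.025 (read as two-sided; not stated), 80% power, ICC 0.03, 20% attrition, about 13 girls in each of 16 groups.

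- Two proportions, pooled null variance, no continuity correction: n = [2.241·√(2·0.38·0.62) + 0.842·√(0.25·0.75 + 0.51·0.49)]² / 0.26² = 64.9, so 65 per arm.
- Retained group size 13 × 0.8 = 10.4; design effect 1 + 9.4 × 0.03 = 1.282.
- Total 2 × 65 × 1.282 / 0.8 = 208.3, against 208 stated.

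The figure reproduces, and nothing below changes it.

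**2. Size of an unclustered test.** The documents give 10-13 girls per group. Assumed: a 5% test level, and that the ICC applies to baseline variables and attrition. Design effect D = 1 + (m − 1) × ICC; size = 2 × [1 − Φ(1.96/√D)].

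| ICC | m = 10 | m = 13 |
|---|---|---|
| 0.01 | D 1.09, 6.1% | D 1.12, 6.4% |
| 0.03 | D 1.27, 8.2% | D 1.36, 9.3% |
| 0.05 | D 1.45, 10.4% | D 1.60, 12.1% |

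At the mean size 208/18 = 11.6 and ICC 0.03, the rate is 8.8%. Simulation at ICC 0.03 with 18 groups of 12 (20,000 runs) gave 8.7% for the t-test, 9.2% for chi-square, and 5.1% for a t-test on group means. For 20% attrition, a separate run (40,000 trials) gave 8.7% unclustered and 4.7% at cluster level. With ten independent baseline variables (an assumption), at least one is flagged 1 − (1 − 0.088)^10 = 60% of the time, against 1 − 0.95^10 = 40%.

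**3. How the baseline value enters.** I read group-by-time as arm-by-time. With two surveys and free baseline means, that effect is a difference in changes. For a linear outcome with within-girl correlation r, relative individual-level variance is 2(1 − r) for change and 1 − r² with baseline as covariate: 1.40 against 0.91 at r = 0.3, 1.00 against 0.75 at 0.5, 0.60 against 0.51 at 0.7.

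Power was simulated for binary outcomes by cluster-mean regression with a t reference: 18 groups, 80% retention, ICC 0.03, 26-point effect, two-sided alpha 0.025. Assumed: r = 0.5 on the latent scale; where site type is modelled, 6 sites per type; in the 35% scenarios, 80% of group variance constant over time.

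| Scenario | Change | Change + site type | Baseline value | Baseline value + site type |
|---|---|---|---|---|
| 25% to 51%, no site-type effect (12 per group, 8,000 trials) | 73.0% | – | 80.2% | – |
| 35% baseline, no site-type effect | 64.1% | 63.0% | 75.7% | 74.0% |
| 35% mean baseline, types at 28/35/42%, total ICC about 0.03 | 67.1% | 65.8% | 78.1% | 78.0% |
| 35% mean baseline, types at 25/35/45%, added to ICC 0.03 | 66.0% | 64.9% | 74.7% | 75.6% |

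The 35% rows use 20,000 trials each. At 25% versus 51% the gain is 80.2 − 73.0 = 7.2 points; a further set of runs gave about 7-8. At 35% the baseline value alone gains 11.6, 11.0 and 8.7 points. In sensitivity runs at 35%, the gain is about 5-7 points at r = 0.7 and about 13-16 at r = 0.3. Null rejection in the 35% scenarios was 2.5-2.6% for change and 2.5-2.8% for baseline value plus site type.

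Mixed logistic models with a Wald z reference (1,000 paired trials each) point the same way: 74.1% against 85.9% without a site-type effect, and 72.3% against 87.6% with one. The z reference is less strict, so the cluster-mean figures are the conservative ones.

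**4. Site type.** From the table, adding it costs 1.1 to 1.3 points in the change contrast. In the baseline-adjusted model it moves power by between −1.7 and a little under +1 point. It helped the change contrast (59.2% to 66.6%) only when trends were assumed to differ by −10/0/+10 points across types, which nothing in the documents supports.

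**5. Completion.** In 40 simulated trials with a linear outcome and completion related to the girl's level, mean arm-by-time was 0.323 without completion and 0.323 with it as a time-constant main effect. It moved to −0.24 when completion was coded to act at follow-up only. A separate simulation gave 0.34 with and without the main effect, falling to about 0.12 when completion did affect the contrast, as in a follow-up model. The size of the distortion depends on the assumed link between completion and outcome level.

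**The case against.** The strongest defence is that the plan already contains much of what is asked for. It has a crude model free of imbalance-selected covariates. The baseline outcome is the first response in the planned model. A model with baseline means constrained equal across arms would also fit the wording. The feasibility section (Aim 1) says the data will inform a later full-scale trial. All of this stands, and it makes the point one of prespecification and efficiency rather than validity.

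A reader might infer more than the documents support:

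- *Covariates will be picked by p-value.* This is a likely reading of the two adjacent sentences, but no such rule or threshold is written, and relevant covariates could include prognostic ones.
- *Baseline outcome data are ignored.* They are not; what is missing is how they enter.
- *The treatment test is inflated.* Nothing here shows that, and simulated null rejection for the models compared stayed near 2.5%.
- *Omitting site type costs power.* The figures show almost no gain and sometimes a small loss. The case for including it is that it stratified the randomization.
- *Adjusting for completion spoils the planned contrast.* As a time-constant main effect it does not. It does when coded to act at follow-up or placed in a follow-up model, and the plan does not state the coding.
- *The trial is underpowered at 208.* The stated calculation reproduces. The lower simulated figures rest on an assumed correlation, a cluster-level t reference and, for the lowest, an assumed 35% prevalence.

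**Conclusion.** The point holds as a matter of prespecification and efficiency. The adjusted model is left to depend on observed imbalance, and the tests used to judge imbalance and attrition state no allowance for the randomized groups. Run unclustered, they would flag chance differences about 8-9% of the time, on the assumptions of a 5% level and an ICC of 0.03 for the variables tested.

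Fixing the baseline value as a covariate would gain about 7-8 power points at the plan's own 25% versus 51%, and about 9-12 at an assumed 35% prevalence. Both ranges assume a within-girl correlation of 0.5 and two-sided alpha 0.025; the gain is smaller at 0.7 and larger at 0.3. The constrained-baseline alternative was not simulated. The change should be made, with medium confidence in the size of the gain.

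**What to change.** Write one adjusted intent-to-treat model per outcome into the plan, to be fitted whatever the baseline table shows:

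- A random group effect, and the baseline value of the outcome in one of two forms: as a covariate in a model of the follow-up value, or through a group-by-time model with baseline means constrained equal across arms. The second form keeps girls lost to follow-up.
- Site type as a fixed covariate, because randomization was stratified by it. In the group-by-time form, include site type by time as well, since the main effect alone gains nothing there.
- No engagement or completion terms. Keep these for the exploratory analyses already planned.
- Baseline characteristics described by arm without tests, and attrition compared with a method that accounts for group, such as a test on group-level proportions or a model with a random group effect.

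The cost is analysis-plan wording only, with no added recruitment or data collection. Site type uses two cluster degrees of freedom and may cost about 1-2 power points if it is not prognostic (75.7% to 74.0% in the simulation). The covariate form uses only girls with both surveys, which matters with 20% attrition planned; the constrained form avoids that.

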We will work with community based programs as well as local schools, and community colleges to conduct recruitment. These partnerships will involve our team going into particular programs or classes to recruit a group of adolescent girls. Given that some group-based programs and/or classes are still virtually held, we will hold orientation sessions either in-person or via zoom. These sessions will include a description of Girls Invest as well as the research study. Among girls who are interested, we will support them to download the app, complete consent forms via the app, and to take the baseline survey. Girls will also complete the savings account application. If parental consent is needed prior to the orientation, we may make arrangements for girls to download the app ahead of the orientation or provide the program with hard copies of the consent form for girls to have parents sign ahead of the orientation day (if in-person)

At schools, our recruitment may also include in-class presentations. Presentations will involve a presentation on financial literacy related topics, including how money and intimate relationships intersect, followed by a brief presentation of our Girls Invest program and study for those who may be interested. We will stay after class if anyone has questions or wants to enroll. The PI will not recruit in any of her own classes at SDSU. We will assure students that participation does not affect their grade in the class.

**Informed consent and data collection.** Informed consent for index participants will occur in-person during a group orientation or via a phone or online chat. The consent forms can be signed with hard copies or via the app. All index participants will be assigned a unique identifier to link baseline and follow-up assessments.

Parental consent will be obtained for those participants between the ages of 15-17 years. After signing the consent form, each eligible participant (<18 years of age) will be provided with two copies of the parental consent form, along with a stamped and addressed envelope, which can be used to mail back the signed parental consent form (one copy of the parental consent will be kept by the parent/guardian). Participants can also choose to do the signed parental consent via

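### Exploring variation in the intervention effect by module completion has no comparable control subgroup (nor does it by study-account saving, if that is what savings behaviors means), so a gradient can reflect who engages

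*Combined protocol and SAP*

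**What the plan says.** The Aim 2 section on statistical power and analyses describes mixed models for the intermediate outcomes "to assess group-by-time effects". It then adds the exploratory sentence at issue: "We will also explore variations in observed intervention effects by savings behaviors, module completion, as well as relevant factors identified via in-depth interview findings".

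Four other parts of the document determine what that sentence can mean.

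- **Informed consent and data collection:** after consent all girls get into the app, but "initially they will only have access to the resource sheet" and the consent forms.
- **Randomization and Retention, programme:** "Control group participants will be notified that they will be on the wait-list and complete the intervention after 6 months".
- **Randomization and Retention, savings account:** the application is open to both arms ("Regardless of study condition, all participants will be linked to the online application for their savings accounts"), but use of the account is not: "For participants in the control group, accounts will become active after the 6 months follow up survey is complete". The recruitment section also places the application at the orientation stage: "Girls will also complete the savings account application".
- **Aim 1 section:** app-generated engagement data are to be collected "and used to identify completers (80% of the" modules), with the other girls classed as non-completers.

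The analysis text gives no method for forming a comparable control group for this exploration, and no caution that the results are non-causal.

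**The concern.** An intervention effect is a contrast between arms. To say that it varies with a characteristic, one needs girls with and without that characteristic in both arms, with the characteristic itself not produced by the arm. Module completion fails both conditions before the 6-month endpoint. Girls who finish most modules probably differ from those who do not, for example in motivation, time or stability, and such differences can move the outcomes without help from the programme.

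Because the plan calls this variation in intervention effects, a self-selected contrast could be reported as a difference in effect, or read as evidence that more modules give more benefit.

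**Working it through.** The plan attaches no figure to this analysis, so there is none to reproduce. The check has three parts.

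**1. What is observable before the 6-month endpoint**

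| Variable | Intervention arm | Control arm | Usable as an effect modifier? |
|---|---|---|---|
| Module completion (80% threshold) | Yes, after randomisation | No, programme comes later | No |
| Saving in the study account after baseline | Yes | No, account inactive | No |
| Saving recorded at baseline, if the survey asks | Yes | Yes | Yes |

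The readable text does not say when savings behaviors are measured, and Figure 1 is not shown.

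**2. The control arm drops out of the contrast**

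Let C, N and W be the mean change from baseline in completers, non-completers and all wait-list controls. Comparing each subgroup with all controls gives effects C − W and N − W. Their difference is (C − W) − (N − W) = C − N. The gradient is therefore a comparison among intervention girls only, and randomisation does not protect it.

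**3. How large a gradient can be with no true effect**

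From the documents: 208 girls, 18 groups (9 per arm), 80% retention, ICC 0.03. Followed girls per group: 208 × 0.80 / 18 = 9.2, taken as 9, so 9 × 9 = 81 in the intervention arm.

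Assumed, because the documents give nothing: a completer gap of 0.3 or 0.5 SD; baseline-to-follow-up correlation r of 0.5 or 0.7; 40% to 80% completing.

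Write g0 and g1 for the completer gap at baseline and follow-up. With equal variances, the change contrast estimates g1 − g0 and the baseline-adjusted contrast estimates g1 − r × g0.

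| How girls select into completion | Change from baseline | Baseline-adjusted |
|---|---|---|
| Stable trait, g0 = g1 = g | 0 | (1 − r)g: 0.3 × 0.3 = 0.09 to 0.5 × 0.5 = 0.25 SD |
| Half the gap at baseline, g0 = g/2, g1 = g | g/2: 0.15 or 0.25 SD | (1 − r/2)g: 0.65 × 0.3 = 0.195 to 0.75 × 0.5 = 0.375 SD |
| Baseline value itself drives completion, g0 = g, g1 = r × g | −(1 − r)g: −0.09 to −0.25 SD | 0 |

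For the half-at-baseline case, the standard error of the within-group change contrast is about √(2(1 − r)) / √(81 × p(1 − p) × 8/9), where p is the proportion completing.

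- Least precise (r = 0.5, p = 0.8): 1 / √11.52 = 0.295.
- Most precise (r = 0.7, p = 0.4 or 0.6): 0.775 / √17.28 = 0.186.
- Gap 0.3: 0.15/0.295 = 0.51 to 0.15/0.186 = 0.81, a rejection rate of about 8% to 13% at nominal two-sided 5%.
- Gap 0.5: 0.25/0.295 = 0.85 to 0.25/0.186 = 1.34, about 14% to 27%.

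Simulation with the ICC included gives 8.0% to 13.2% and 13.0% to 27.0%. At the plan's type I error of 0.025, the same case rejects about 5% to 8% and 9% to 18%. In the third row of the table, the change contrast rejects in about 7% to 18% of trials at 5%, while the adjusted contrast stays near 5%.

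**The case against.** The strongest defence is that the sentence says only that effects will be explored, mentions no dose-response claim, and has no decision attached to it. A within-arm description would be compatible with it. That stands, and it sets the severity. It does not supply the missing comparison: as worded, the result would still be labelled variation in intervention effects.

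A second defence is that the group-by-time model already handles selection. It does so only for the part of the gap that persists unchanged from baseline. If baseline values drive completion, the change contrast creates a gradient through regression to the mean. A reader might infer the reverse rule, that baseline adjustment should be avoided because it leaves part of a stable gap. The documents do not support that either. They do not say how girls come to complete, and each analysis is near zero under one mechanism and biased under another.

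A third defence is that controls receive the same programme later, so their completion might eventually be known. A reader might infer that the control completers can never be identified; that goes too far. Later completion, after a 6-month wait, could serve as a proxy, but an imperfect one, and the plan does not commit to using it.

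A fourth is that the plan says savings behaviors, not study-account saving. This also stands in part. A reader might infer that every savings analysis is invalid, but saving recorded at baseline in both arms would be a legitimate modifier. The account application is also open to both arms, although the Aim 1 section lists account enrolment under adherence.

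Finally, the magnitudes rest wholly on assumed gaps, correlations and completion rates. That is accepted.

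**Conclusion.** The point holds for module completion. It holds for savings behaviors only where they mean post-baseline saving in the study account. For these variables the planned exploration cannot separate a varying effect from who engages.

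The size is not derivable from the documents. Under the stated assumptions and no true effect, the spurious gradient in change runs from about zero (stable trait) to 0.15 or 0.25 SD (half the gap at baseline), and to between −0.09 and −0.25 SD (baseline-driven completion). The 8% to 27% rejection range illustrates the half-at-baseline case and is not an estimate for this trial.

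Severity is minor. A reader might infer that this sentence undermines the trial's main result; it does not, because the randomised comparison of arms does not depend on it. The plan's separate statement that the main models adjust for engagement and completion is a different matter, not argued here.

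**What to change.** In the Aim 2 analysis text:

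1. Replace effect variation by module completion, and by post-baseline study-account saving, with a description of outcomes by completion or saving level within the intervention arm. Allow for clustering and label it descriptive and non-causal. Show both change from baseline and baseline-adjusted results, since each can give a spurious gradient under a different selection mechanism. Agreement between them would not make the result causal.
2. Reserve the term variation in intervention effect for characteristics measured at baseline in both arms, including baseline saving if the survey records it. Applying this rule to savings means stating when savings behaviors are measured.

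The cost is a few sentences and a small amount of extra analysis, with no new data collection. The downside is a weaker claim about dose-response.
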